10.3.2 Definition of SAE

An SAE is defined as any serious AE that, at any dose:

• Results in death

Is life-threatening

The term 'life-threatening' in the definition of 'serious' refers to an event in which the subject was at risk of death at the time of the event. It does not refer to an event, which hypothetically might have caused death, if it were more severe.

• Requires inpatient hospitalization or prolongation of existing hospitalization

- In general, hospitalization signifies that the subject has been admitted (usually involving at least an overnight stay) at the hospital or emergency ward for observation and/or treatment that would not have been appropriate in the physician's office or outpatient setting. Complications that occur during hospitalization are AEs. If a complication prolongs hospitalization or fulfills any other serious criteria, the event is serious. When in doubt as to whether "hospitalization" occurred or was necessary, the AE should be considered serious.
- Hospitalization for elective treatment of a pre-existing condition that did not worsen from Baseline is not considered an AE.

• Results in persistent or significant disability/incapacity

- The term disability means a substantial disruption of a person's ability to conduct normal life functions.
- This definition is not intended to include experiences of relatively minor medical significance such as uncomplicated headache, nausea, vomiting, diarrhea, influenza, and accidental trauma (e.g., sprained ankle) which may interfere with or prevent everyday life functions but do not constitute a substantial disruption.

• Is a congenital anomaly/birth defect

• Other situations:

- Medical or scientific judgment should be exercised by the Investigator in deciding whether SAE
 reporting is appropriate in other situations such as significant medical events that may jeopardize the
 subject or may require medical or surgical intervention to prevent one of the other outcomes listed in the
 above definition. These events should usually be considered serious.
- Examples of such events include invasive or malignant cancers, intensive treatment for allergic bronchospasm, blood dyscrasias, convulsions, or development of intervention dependency or intervention abuse.

10.3.3 Recording and Follow-Up of AE and/or SAE

AE and SAE Recording

- When an AE/SAE occurs, it is the responsibility of the Investigator to review all documentation (e.g., hospital progress notes, laboratory reports, and diagnostics reports) related to the event.
- The Investigator will then record all relevant AE/SAE information.
- It is **not** acceptable for the Investigator to send photocopies of the subject's medical records to the Sponsor or designee in lieu of completion of SAE/AE required form.
- There may be instances when copies of medical records for certain cases are requested by the Sponsor or designee. In this case, all subject identifiers, with the exception of the subject number, will be redacted on the copies of the medical records before submission to the Sponsor or designee.
- The Investigator will attempt to establish a diagnosis of the event based on signs, symptoms, and/or other clinical information. Whenever possible, the diagnosis (not the individual signs/symptoms) will be documented as the AE/SAE.

Assessment of Intensity

The Investigator will make an assessment of intensity for each AE and SAE reported during the study and assign it to one of the following categories:

- Mild: An event that is easily tolerated by the subject, causing minimal discomfort and not interfering with everyday activities.
- Moderate: An event that causes sufficient discomfort to interfere with normal everyday activities.
- Severe: An event that prevents normal everyday activities. An AE that is assessed as severe should not be confused with an SAE. Severe is a category utilized for rating the intensity of an event; and both AEs and SAEs can be assessed as severe.
- An event is defined as 'serious' when it meets at least one of the predefined outcomes as described in the definition of an SAE, NOT when it is rated as severe.

Assessment of Causality

- The Investigator is obligated to assess the relationship between study intervention and each occurrence of each AE/SAE.
- A "reasonable possibility" of a relationship conveys that there are facts, evidence, and/or arguments to suggest a causal relationship, rather than a relationship cannot be ruled out.
- The Investigator will use clinical judgment to determine the relationship.
- Alternative causes, such as underlying disease(s), concomitant therapy, and other risk factors, as well as the temporal relationship of the event to study intervention administration will be considered and investigated.
- The Investigator will also consult the IB and/or Product Information, for marketed products, in his/her assessment.
- For each AE/SAE, the Investigator **must** document in the medical notes that he/she has reviewed the AE/SAE and has provided an assessment of causality.
- There may be situations in which an SAE has occurred, and the Investigator has minimal information to include in the initial report to Attralus, Inc. However, it is very important that the Investigator always make an assessment of causality for every event before the initial transmission of the SAE data to Attralus, Inc.
- The Investigator may change his/her opinion of causality in light of follow-up information and send an SAE follow-up report with the updated causality assessment.
- The causality assessment is one of the criteria used when determining regulatory reporting requirements.

Follow-up of AEs and SAEs

- The Investigator is obligated to perform or arrange for the conduct of supplemental measurements and/or evaluations as medically indicated or as requested by Attralus, Inc to elucidate the nature and/or causality of the AE or SAE as fully as possible. This may include additional laboratory tests or investigations, histopathological examinations, or consultation with other health care professionals.
- If a subject dies during participation in the study or during a recognized follow-up period, the Investigator will provide Attralus, Inc with a copy of any postmortem findings including histopathology.
- New or updated information will be recorded in the originally submitted documents.
- The Investigator will submit any updated SAE data to Attralus, Inc within 24 hours of receipt of the information.

10.3.4 Reporting of SAEs

SAE Reporting to Attralus, Inc. via the Electronic Data Collection (EDC) System

- The primary mechanism for reporting an SAE to Attralus, Inc. will be the EDC system.
- If the EDC system is unavailable, then the site will use the paper SAE data collection tool (see next section) to report the event within 24 hours.
- The site will enter the SAE data into the EDC system as soon as it becomes available.
- After the study is completed at a given site, the EDC system will be taken off-line to prevent the entry of new data or changes to existing data.
- If a site receives a report of a new SAE from a study subject or receives updated data on a previously reported SAE after the EDC system has been taken off-line, then the site can report this information as noted in the Study Manual.
- Contacts for SAE reporting can be found in the Study Manual.

SAE Reporting to Attralus, Inc. via Paper Data Collection Tool

- It is the responsibility of the Investigator to report SAEs to the Sponsor within 24 hours of awareness of the event or safety information, whether initial or follow-up. Do not delay in the reporting of suspected SAE in order to obtain additional information. Any additional information, if collected, can be reported to the Sponsor as a follow-up to the initial report.
- In rare circumstances and in the absence of facsimile equipment, notification by telephone is acceptable with a copy of the SAE data collection tool sent by overnight mail or courier service.
- Initial notification via telephone does not replace the need for the Investigator to complete and sign the SAE data collection tool within the designated reporting time frames.
- Contacts for SAE reporting can be found in the Study Manual.

10.4 Appendix 4: Contraceptive and Barrier Guidance

10.4.1 Definitions

Women of Childbearing Potential (WOCBP)

A woman is considered fertile following menarche and until becoming postmenopausal unless permanently sterile (see below).

If fertility is unclear (e.g., amenorrhea in adolescents or athletes) and a menstrual cycle cannot be confirmed before first dose of study intervention, additional evaluation should be considered.

Women in the following categories are not considered WOCBP:

- Premenarchal; or
- Premenopausal female with one of the following:
 - Documented hysterectomy
 - Documented bilateral salpingectomy
 - Documented bilateral oophorectomy

For individuals with permanent infertility due to an alternate medical cause other than the above, (e.g., Müllerian agenesis, androgen insensitivity), Investigator discretion should be applied to determining study entry.

Note: Documentation can come from the site personnel's: review of the subject's medical records, medical examination, or medical history interview.

Postmenopausal Female

A postmenopausal state is defined as no menses for 12 months without an alternative medical cause.

A high follicle stimulating hormone (FSH) level in the postmenopausal range may be used to confirm a postmenopausal state in women not using hormonal contraception or hormone replacement therapy (HRT). However, in the absence of 12 months of amenorrhea, confirmation with more than one FSH measurement is required. The Screening Visit FSH will be processed using the chemistry tube and the Day 1 FSH will need to be collected separately and sent to the central lab for analysis. A pregnancy test is required until both FSH measurements have been collected and results have been received that verify the postmenopausal state of the female subject.

Females on HRT and whose menopausal status is in doubt will be required to use one of the non-estrogen hormonal highly effective contraception methods if they wish to continue their HRT

during the study. Otherwise, they must discontinue HRT to allow confirmation of postmenopausal status before study enrollment.

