1.3 Schedule of Activities

| Visit | Screening | Vis Da | it 1/ y 1 | | it 2/ ek 6 | Safety Follow-up 1 ^j | Safety Follow-up 2 (EOS) ^j | Early Termination (ET) k,l |
|--|------------------------|---------------------------------|------------------------------------|---------------------------------|------------------------------------|------------------------------------|---|--------------------------------|
| Window | Day -30 to Day 1 | ± 0 | days | Week 6 t | o Week 8 | 1-3 Days After Visit 2 | 28 (± 3) Days After Visit 2 | <7 days from ET Decision |
| Timing of Activity(ies) | | Prior to ¹²⁴ I-AT-01 | ¹²⁴ I-AT-01 and Scan | Prior to ¹²⁴ I-AT-01 | ¹²⁴ I-AT-01 and Scan | | | |
| Assessment/Procedures | | | | | | | | |
| Informed Consent a | X | | | | | | | |
| Medical history and Demographics | X | | | | | | | |
| Inclusion and Exclusion criteria | X | | | | | | | |
| Concomitant Medications | X | X | X | X | X | X | X | X |
| Oral Potassium Iodide (KI) ^b | | X | | X | | | | |
| ¹²⁴ I-AT-01 Administration ^c | | | X | | X | | | |
| Biomarker and Safety Assessments | | | | | | | | |
| Vital Signs (HR and BP) d | | X | X | X | X | | | |
| Body Weight | | X | | X | | | | |
| Height | | X | | | | | | |
| Pregnancy Test (WOCBP) e,f | X | | | X | | | | |
| PET/CT Scan | | | X | | X | | | |
| Adverse events g | X | X | X | X | X | X | X | X |
| Laboratory h,i | X | | | X | | X | | |
| Biomarkers h,i | X | | | X | | | | |
| Urine UACR (AL subjects only) i | X | | | X | | | | |
| Serum ADA i | X | | | X | | | X | X |

Abbreviations: ADA = anti-drug antibodies; AL = amyloid light chain amyloidosis; BP = blood pressure; CBC = complete blood count; EOS = end of study; ET = early termination; HR = heart rate; NT-proBNP = N-terminal prohormone of brain natriuretic peptide; UACR = urine albumin-to-creatinine ratio; WOCBP = women of childbearing potential.

- a. Informed consent, as described in Section 10.1.3.
- b. KI is self-administered by the subject daily for 3 days, beginning >30 minutes and <24 hr prior to dosing, as described in Section 4.1.2.
- c. ¹²⁴I-AT-01 will be administered by IV infusion over 2-5 minutes (protocol Version 1.1) or slow IV bolus at 1 mL/5 seconds (protocol Version 2.0), as described in Section 4.1.3. For all subjects, ¹²⁴I-AT-01 will be administered by the same route (IV infusion over 2-5 minutes or slow IV bolus at 1 mL/5 seconds) at the Week 6 visit as on the Day 1 visit.

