- d. Subjects must remain semi-recumbent for at least 5 minutes prior to blood pressure measurements. Blood pressure and heart rate will be measured within an hour prior to dosing and 5-10 minutes after administration of ¹²⁴I-AT-01.
- e. Serum pregnancy test, as indicated in Section 10.2, will be obtained in all women of childbearing potential.
- f. Serum pregnancy and all other laboratory samples must be drawn within 7 days prior to administration of ¹²⁴I-AT-01 in all WOCBP. The results of the pregnancy test must be available and be negative prior to ¹²⁴I-AT-01 administration in all WOCBP.
- g. Adverse events will be monitored from Screening through the EOS Visit. For Safety Follow-up 1 and 2, adverse events and concomitant medications can be obtained by phone call.
- h. Clinical laboratory tests and biomarker analysis, as described in Section 10.2. Baseline sample will be collected within 30 days prior to the first administration of ¹²⁴I-AT-01; second sample within 7 days prior to the second administration of ¹²⁴I-AT-01; third sample at Safety Follow-up 1 after the second administration of ¹²⁴I-AT-01.
- i. Urine and blood may be collected locally by visiting nurse/phlebotomist. An additional serum ADA sample will be obtained at Screening for subjects who provided consent for the extra ADA sample.
- j. Safety follow-ups for concomitant medications and adverse events will be done via telephone call for all subjects. Both Safety Follow-up 1 and Safety Follow-up 2 activities will be conducted for subjects who discontinue for IRRs at either the first or second administration of ¹²⁴I-AT-01.
- k. Blood draw for ADA should be obtained if ET is ≥4 weeks after first administration of ¹²⁴I-AT-01.
- l. Early Termination activities do not apply to subjects discontinued for IRRs. Please follow Safety Follow-up 1 and Safety Follow-up 2 activities for subjects experiencing IRR with either the first or second administration of ¹²⁴I-AT-01.

- 15 -

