4.1.3 Administration Period

Administration of ¹²⁴I-AT-01 and the associated study procedures occur at the Day 1 and Week 6 (+ 2 week) visits. Administration of ¹²⁴I-AT-01 and the associated study procedures are described in Section 4.1.3.1.

4.1.3.1 Administration of Study Intervention(s) and Associated Procedures Day 1 and Week 6 (+ 2 week) Visits

The schedule for administration of ¹²⁴I-AT-01 is provided in the SoA (Section 1.3). Administration of ¹²⁴I-AT-01 occurs at the Day 1 and Week 6 to Week 8 visits, as follows:

Prior to Administration of ¹²⁴I-AT-01

- 1) Clinical laboratory tests and biomarker analysis (including serum pregnancy test in WOCBP) will be obtained within 7 days prior to the second administration of ¹²⁴I-AT-01, as described in the SoA (Section 1.3). The results of the pregnancy test must be available and be negative prior to ¹²⁴I-AT-01 administration in all WOCBP.
- 2) Instruct subject to take oral KI daily for 3 days, as described in Section 4.1.2.
- 3) Record concomitant medications and monitor and record AEs throughout the study visit.

Administration of ¹²⁴I-AT-01

4) Subjects enrolled under protocol Version 2.0 will receive a single dose of 1 mCi (± 10%) 124I-AT-01 by slow IV bolus at a rate of 1 mL/ 5 seconds. During 124I-AT-01 administration, monitor subjects for infusion-related reactions (IRRs), as described in Section 7.1.1. For all subjects, 124I-AT-01 will be administered by the same route (IV infusion over 2-5 minutes or slow IV bolus at 1 mL/5 seconds) at the Week 6 visit as on the Day 1 visit.

After Completion of Administration of ¹²⁴I-AT-01

- 5) Blood pressure and heart rate will be measured 5-10 minutes after administration of ¹²⁴I-AT-01.
- 6) Subjects will undergo a PET/CT scan 5 hours (± 30 minutes) after the start of administration of ¹²⁴I-AT-01 to quantify ¹²⁴I-AT-01 uptake in organs. ¹²⁴I-AT-01 whole-body scans will be acquired by study-designated PET/CT scanners, as described in Section 8.1.4.
 - Subjects will be discontinued if amyloid deposits are not identified in the Day 1 PET/CT scan in at least one of the following organs: heart, liver, spleen or kidney (i.e., they will not receive a second administration of ¹²⁴I-AT-01 or undergo a second scan) and will undergo early termination (ET) activities, as provided in the SoA (Section 1.3) and as described in Section 4.1.5.
- 7) Any adverse events will be recorded; patient can be discharged after completing the scan and deemed stable by study staff.

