7.0 DISCONTINUATION OF STUDY INTERVENTION AND/OR SUBJECT DISCONTINUATION OR WITHDRAWAL

7.1 Discontinuation of Study Intervention

All subjects are free to withdraw from participating in this study at any time for any reason, specified or unspecified, and without prejudice. No constraints will be placed on ordinary subject management.

Subjects will be withdrawn for any of the following reasons:

- The subject withdraws consent.
- The subject does not have amyloid deposits in the heart, liver, spleen or kidney on the Day 1 PET/CT scan, as described in Section 8.1.4.
- The subject begins treatment with heparin or a heparin analog within 7 days of a planned administration of ¹²⁴I-AT-01, as described in Section 7.1.1.2.
- The subject experiences an intolerable AE or serious AE (SAE).
- The subject enrolls into another clinical study in which an investigational treatment or approved therapy for investigational use is administered.
- The subject becomes pregnant. Study treatment must be discontinued immediately. Report the pregnancy according to the instructions in Section 8.3.5.
- The subject is unwilling or unable to comply with the protocol.
- At the discretion of the Investigator or Sponsor.
- Investigator decision that it is not in the best medical interest of the subject to continue participation in the investigation.
- The Sponsor prematurely terminates the study.

Prior to discontinuing a subject, every effort should be made to obtain as much follow-up data as possible. Withdrawn or discontinued subjects will undergo ET activities per the SoA (Section 1.3). Subject withdrawals will be documented clearly on the source documents and applicable case report forms (CRFs). Subject withdrawals will be documented clearly on the source documents and applicable CRFs.

Discontinued subjects will be assessed for adverse events via a telephone call 24-48 hours after decision to discontinue.

Notification of subject withdrawals will be made to the Sponsor, or designee.

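### Section 10.4.1 lets two FSH results end pregnancy testing before the second 124I dose in a woman whom criterion 5a still classes as of childbearing potential (minor)

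*Protocol*

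**What the plan says.** Protocol 10.4.1 defines the postmenopausal state as 12 months without menses and no other medical cause. It then opens a second route. A high FSH may be used as confirmation in women who use neither hormonal contraception nor HRT, but "in the absence of 12 months of amenorrhea, confirmation with more than one FSH measurement is required". On timing, "The Screening Visit FSH will be processed using the chemistry tube and the Day 1 FSH will need to be collected separately" and goes to the central laboratory. The paragraph ends: "A pregnancy test is required until both FSH measurements have been collected and results have been received that verify the postmenopausal state".

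Inclusion criterion 5a (section 5.1) and item (a) of 10.4.2 define childbearing potential differently. A postmenarchal woman leaves that class only through at least 12 months of amenorrhea or surgical removal of ovaries or uterus. Neither mentions FSH. Both allow the definition to be adapted to local guidelines or requirements.

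Section 8.2.3 requires a negative test before both doses in women of childbearing potential and takes the definition from Appendix 4, which contains both 10.4.1 and 10.4.2(a). The Schedule of Activities (row "Pregnancy Test (WOCBP) e,f") places tests at Screening and Week 6 only. Its footnote f sets the age limit for these women: "Serum pregnancy and all other laboratory samples must be drawn within 7 days prior to administration of" the tracer. Section 4.1.3.1 repeats this for dose 2: "Clinical laboratory tests and biomarker analysis (including serum pregnancy test in WOCBP) will be obtained within 7 days prior to the second administration". Section 7.1 lists pregnancy as a reason for withdrawal: "The subject becomes pregnant. Study treatment must be discontinued immediately".

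**The concern.** The protocol gives two answers for the same woman. Under 10.4.1 her testing can stop once both FSH results are in and verify menopause. Under 5a and 10.4.2(a) she is still of childbearing potential, so 8.2.3 requires a test within 7 days before dose 2. No sentence says which provision prevails.

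The test at stake is the only scheduled procedure that would detect a pregnancy between the two 124I doses, and 7.1 makes pregnancy an immediate stop. On the 10.4.1 reading it is dropped on the strength of two FSH samples for which no minimum interval is stated, although the same section defines menopause as 12 months without menses. The same conflict leaves open whether the contraception agreement in criterion 5 applies to her. Each dose carries an estimated 8.7 mSv whole-body effective dose to the subject (section 2.3.2.1). That figure is not a fetal estimate.

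**Working it through.** **1. How the documents count weeks.** SAP Table 8-1 gives Day 43 as the target for Visit 2 / Week 6: 1 + 6 × 7 = 43, which agrees. Protocol 4.2.3 justifies the gap as ten half-lives: 10 × 4.2 days = 42 days = 6 weeks, which also agrees.

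**2. Which test can be dropped.** Tests are scheduled at Screening and Week 6. The second FSH is drawn on Day 1 and must travel to the central laboratory, and testing is required until that result is received. The test before dose 1 is therefore unaffected. Only the Week 6 test can fall away.

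**3. Age of the last test at dose 2.** Inputs:
- Dose 2 is given at Week 6 to Week 8 (section 4.1.3.1), which is 42 to 56 days after Day 1.
- The test before dose 1 is 0 to 7 days old on Day 1 (section 8.2.3; Schedule of Activities, footnote f).

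Age at dose 2 = days between doses + age of the test on Day 1.
- Lowest: 42 + 0 = 42 days.
- Highest: 56 + 7 = 63 days.

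If Week 8 were read as running to the end of that calendar week, six days would be added, giving 69 days. Under 5a or 10.4.2(a) the age would be 0 to 7 days. The calculation assumes that the Day 1 FSH result is back before the Week 6 test is due. No turnaround time is given, but the test window opens no earlier than 42 − 7 = 35 days after Day 1.

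**4. Interval between the FSH samples.** 10.4.1 states none. If footnote f is applied to this woman, the samples are 0 to 7 days apart. Under the general Screening window they are 0 to 30 days apart. Both are inferences from the visit windows.

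**5. Size of the risk.** Take the contraceptive failure ceiling in criterion 5, 1% per year, and assume that contraception is kept. The chance of pregnancy over d days is 1 − 0.99^(d/365.25).
- d = 42: 0.00116, or 0.12%.
- d = 63: 0.00173, or 0.17%.

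The documents do not say how many women would qualify. Assuming 0 to 3 among up to 20 subjects, the expected number of pregnancies is between 0 and 3 × 0.00173 = 0.0052. No credit is given here for the two FSH results, which would lower the figure. If contraception is not kept, the figure does not apply and is not a bound.

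**The case against.** The strongest reply is that the sponsor made a deliberate and cautious choice. One FSH value is not enough, women on hormonal contraception or HRT are outside the route, and testing continues until both results are received and verify menopause. 10.4.1 carries the heading for definitions and holds the only sentence on when testing ends, whereas 10.4.2(a) sits under contraception guidance. It is natural to let 10.4.1 govern testing. The clause on local adaptation also gives some room.

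That reading is reasonable, but it does not remove the problem. It is the reading on which the check between doses is skipped, for a woman whom the inclusion criterion treats as potentially fertile. The adaptation clause concerns local guidelines and does not mention FSH or settle precedence.

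The reply is right that the chain of conditions is long. She must have under 12 months of amenorrhea, use no hormonal contraception or HRT, have two confirming FSH values returned in time, and attend a site that then omits the test. The Schedule of Activities and the laboratory table in 10.2 do not list FSH, so a site working only from those would have no prompt to stop testing.

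A reader might infer more than the documents support:
- *That dose 2 would break the 7-day limit by a factor of 6 to 9.* The ratio (42/7 to 63/7) is arithmetically right, but the limit applies to women of childbearing potential, and her classification is the point in dispute.
- *That 0.12 to 0.17% is a ceiling on the risk.* It rests on contraception being kept, and whether that agreement still binds her under 10.4.1 is unresolved.
- *That dose 1 is also exposed.* It is not, as step 2 of the working shows.

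**Conclusion.** The inconsistency is real and minor. 10.4.1 can end pregnancy testing before dose 2 for a woman whom 5a and 10.4.2(a) still class as of childbearing potential, so two sites could treat her differently and each point to protocol text. The consequence on one reading is a last test 42 to 63 days old at dose 2, against 0 to 7 days on the other.

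Few or no subjects are likely to be affected; the 0 to 3 used in the working is an assumption. The chance of pregnancy is about 0.1 to 0.2% per woman, conditional on contraception at the 1% per year ceiling. No repeatability result changes. The documents do not support reading this as a serious safety failure. The case for a change is that it is cheap and removes an ambiguity about testing before a radioactive dose.

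**What to change.** Keep the FSH sentences in 10.4.1, including the need for more than one measurement. Replace only the last sentence of that paragraph with:

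*A woman with under 12 months of amenorrhea whose postmenopausal state rests on FSH results must still have a negative serum pregnancy test drawn within 7 days before each 124I-AT-01 dose. For testing and contraception she remains of childbearing potential as in criterion 5a and section 10.4.2(a).*

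The first sentence makes the test at dose 2 at most 7 days old whichever definition a site follows. The second reconciles the definitions and settles whether the contraception agreement applies. Women with 12 months of amenorrhea or documented surgical sterility are not affected.

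The cost is two sentences in one appendix and, for each such woman, one serum hCG on the blood draw already scheduled before dose 2. There is a small chance that a false positive delays or cancels dose 2 and loses one scan pair out of up to 20. The protocol already accepts that chance for every other woman of childbearing potential.
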